1.0 Study Summary

Study Title	Multi-level Intervention to Reduce Pregnancy Risk Among Adolescents: A Feasibility Trial in the Emergency Department
Study Design	
Randomized Clinical Trial
 
This project will involve human subjects in a clinical trial conducted at Children's Mercy (CM) and the Children's Hospital of Philadelphia (CHOP). We will train advanced practice practitioners to deliver the contraception intervention to adolescents and both practitioners and adolescents will complete surveys after the intervention. After recruitment for the intervention is completed, we will conduct interviews with key stakeholders at each institution. CM will be the primary site and CHOP will ultimately seek reliance on our IRB.

Primary Objective	Conduct a randomized clinical trial to evaluate intervention feasibility constructs: acceptability, demand, implementation, practicality, adaptation, integration, expansion, and limited-efficacy.
Secondary Objective(s)	NA
Research Intervention(s)/Investigational Agent(s)	We will evaluate our novel approach to increase access to contraception comparing our multi-level intervention (MLI) to enhanced standard of care (eSOC). All adolescents receive the MI-enhanced counseling and clinic referral. Those randomized to MLI will be offered immediate, ED-based contraception (i.e., oral pill, transdermal patch, vaginal ring, injection, subdermal implant) in addition to receive a warm referral (provider helping to schedule follow-up appointment) to follow-up on selected method (or to initiate in clinic, if preferred). Per usual care, eSOC participants may obtain contraception only at the referral.
IND/IDE #	NA
Study Population	
Adolescents: Females (assigned at birth) aged 15-18 years who report past/anticipated intercourse with a male, do not desire pregnancy, and are not using hormonal contraception/copper IUD.
 
Personnel: Study providers including advanced practice practitioners (APPs) and pediatricians, adolescent medicine specialists, and nursing/administrative leaders.

Sample Size	
Adolescents: 98 (49 CMH/49 CHOP)
 
Personnel: study providers = 30 (15 CMH/15 CHOP); other organizational personnel (OOP) = 30 (15 CMH/15CHOP)

SHORT TITLE: Reducing Pregnancy in the ED

Study Duration for Individual Participants	
Adolescents: 6 months
 
Personnel: Study providers will participate for the duration of training and adolescent recruitment; other personnel are involved only once in the study (about 60-90 minutes).

Study Specific Abbreviations/Definitions	
MLI = multi-level intervention
 
eSOC = enhanced standard of care
 
IUD = intrauterine device
 
ED = emergency department
 
APP = advanced practice practitioner
 
OOP = other organizational personnel
 
EMR = electronic medical record
 
CHOP=Children's Hospital of Philadelphia
 
CM= Children's Mercy

2.0 Objectives

Evaluate intervention feasibility constructs: acceptability, demand implementation, practicality, adaptation, integration, expansion, and limited-efficacy. We will conduct a small randomized trial to assess feasibility and use mixed-methodology to explore contextual factors at the patient, provider, and system levels. In evaluating limited-efficacy, we compare two arms (MLI vs. eSOC) to determine size of effect rates on contraception initiation.

Hypothesis 1.1: The intervention will be deemed feasible by stakeholders: adolescents and organizational personnel (i.e., study providers, adolescent medicine specialists, hospital nursing and administrative leaders).

Hypothesis 1.2: Adolescents in the MLI arm will have greater contraception initiation rates relative to the eSOC arm at 30 days after the index ED visit.

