4.0 Study Endpoints

The primary endpoint will be the determination of feasibility. Methods for establishing feasibility vary and include levels of acceptability, satisfaction, or usefulness. Drawing on similar published criteria, the intervention will be deemed feasible if the average score across all items is ≥ 3 on closed-ended survey items for adolescents, providers, and OOPs (Table 1).

Secondary endpoints will include the following:

- The completion of a referral for any contraceptive care as assessed through EMR review or follow-up phone calls.
- The initiation of contraception as assessed through EMR review or follow-up phone calls.
- Saturation of themes from qualitative interviews that have been coded and analyzed.

Hypotheses 1.1 and 1.2: To establish feasibility, we assess multiple constructs via survey items among all stakeholders (Table 1).

Hypotheses 1.2: We will determine referral completion and date for contraception initiation (Time 0) via participant contact and review of study/medical records at thirty days after the index visit.

Table 1: Mixed-Methodology Feasibility Assessment with Adolescent and Personnel Stakeholders

Construct	Source	Index Visit: Post-intervention	Time from Index Visit	Time from Initiation (Time 0)		
			30 Days*	3 mos*	6 mos*	
Acceptability - How do stakeholders react to the intervention?	Adolescent	S	S	S	S	
	Providers	S			SSI	
	Other personnel				S, SSI	
Demand - To what extent is the innovation likely to be used?	Providers				S, SSI	
	Other personnel				S, SSI	

SHORT TITLE: Reducing Pregnancy in the ED

	Study/Medical Record*				SMRR
Implementation - To what extent can the intervention be implemented as planned (including intervention fidelity)?	Providers	S			SSI
	Other personnel				S, SSI
	Study/Medical Record*	SMRR	SMRR		
Practicality - What factors make intervention delivery challenging or facilitate delivery?	Providers	S			S, SSI
	Other personnel				S, SSI
	Study/Medical Record*				SMRR
Adaptation – How does model perform in new setting?	Providers				SSI
	Study/Medical Record*				SMRR
Integration - To what extent can model be integrated within the system?	Providers				S, SSI
	Other personnel				S, SSI
Expansion - To what extent can model be expanded to provide service?	Providers				S, SSI
	Other personnel				S, SSI
	Study/Medical Record*				SMRR
Limited efficacy testing - What are rates of contraception initiation/continuation and referral completion?	Adolescent		S	S	S
	Study/Medical Record*	SMRR			SMRR

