All participants receive contraceptive counseling. Per evidence-based guidelines,⁵²⁻⁵³ MLI participants can receive contraception (one injection, three-month supply of pill/patch/ring, or subdermal implant) in the ED, or prescription for another method if desired. If a patient in this group desires another method that is not being covered by the study, patient will be made aware of their responsibility to cover the cost of the medication either out of pocket, or by using their own insurance. Due to credentialing and staffing constraints, intrauterine devices will only be available at referral clinics. MLI participants who want to initiate contraception must complete a urine pregnancy test, which must be negative. MLI participants who initiate contraception will be given a take home pregnancy test that is to be completed two weeks after enrollment. eSOC participants will have the opportunity of being referred to a follow-up appointment to discuss and begin contraception. Subjects in this group will not begin contraception in the Emergency Department or given a prescription. All participants will be referred to an adolescent gynecologist, hospital-affiliated adolescent clinic, or Title X clinic for additional care and to initiate or follow-up on contraception.

MLI participants will have a “warm transfer” to follow-up on or initiate, if preferred, selected method. Warm transfers occur with the assistance of a provider scheduling the follow-up appointment. Doing this in such a way should help to minimize barriers with navigating the healthcare system. The provider will share detailed clinic information including hours of operation and contact the receiving site. We will assist with scheduling (sending multiple reminders) and transportation. eSOC participants will be given printed information on clinics.

C6eiii. Intervention Fidelity: Counseling sessions will be audio-recorded and reviewed periodically to ensure for fidelity to content and use of MI strategies using a tool adapted from our previous work and the CHOICE Project, a clinic-based intervention efficacious for increasing contraception uptake in family-planning clinics.⁵⁴⁻⁵⁵ We will provide feedback to individual APPs if mean fidelity score ≤ 3 .

SHORT TITLE: Reducing Pregnancy in the ED

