11.0 Inclusion and Exclusion Criteria

Study APPs

Inclusion Criteria

1. Work in the Emergency Department
2. Are interested in participating in study procedures

Exclusion Criteria

1. Because they often lack organizational familiarity and may be temporarily working in the ED, providers in training will be excluded.
2. AP provider who were otherwise eligible, but have declined to participate in training activities.

Adolescents

Inclusion Criteria

1. Females aged 15-18 years who are at risk of pregnancy, defined as those who 1) report previous sexual activity or intent to be sexually active with a male partner in the next few months, 2) do not desire pregnancy within the next year, and 3) are not currently using hormonal contraception or copper IUD.
2. Eligible individuals must be comfortable speaking in English

Exclusion Criteria

1. Females who are currently using hormonal contraception or the copper intrauterine device
2. Females who report current pregnancy or have positive urine pregnancy test
3. Patient has a developmental delay limiting participation
4. Patients is presenting in the ED after sexual assault
5. Patient is too ill to be screened
6. Minor adolescent who is ward of the state is eligible to enroll for the study but may not be eligible for Nexplanon insertion (if desired) unless proper parental or legal guardian permission is obtained (Nexplanon insertion is not available without parental or legal guardian permission due to hospital guidelines. Without the proper consent, wards of the state may opt for another form of contraception)
7. Patients who receive contraceptive medications as part of their Emergency Department clinical care (e.g., treatment for heavy menses).

Other Organizational Personnel

Inclusion Criteria

1. Employed at CM or CHOP with experience or expertise in hospital administration, adolescent medicine, or clinical care
2. Are interested in participating in study procedures

Exclusion Criteria

SHORT TITLE: Reducing Pregnancy in the ED

- 1 . Provider/staff who were otherwise eligible, but have declined to participate in training activities.

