## Statistical analysis plan

We used R software (R Foundation for Statistical Computing) for analyses. In keeping with guidance discouraging the use of “statistical significance” and binary hypothesis testing based on arbitrary cutoffs (e.g.,  $P < .05$ ), we examined effect sizes along with  $P$  values and include  $P$  values without describing them as “significant” or “not significant.” Consistent with this approach, we did not attempt to control the familywise error rate (probability of at least one type I error across the study), which is not defined outside of binary hypothesis testing. We summarized closed-ended feasibility outcomes using descriptive statistics. We used an intention-to-treat analysis to assess preliminary efficacy and Fisher exact tests to compare arms on the percent of participants using contraception at 30 days. Dropouts during the index visit were treated as having no subsequent contraceptive use. Differences in average change score (e.g., attitudes) between arms were tested using nonparametric permutation tests.

*Primary Outcome:* We hypothesized the intervention would be deemed feasible by stakeholders. Drawing on similar examples in the literature, we determined a priori that the intervention would be feasible if the mean score across five Likert-scale survey items was  $\geq 4$  (range 1-5).

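### Hypothesis 1.2 concerns contraception initiation, determined at 30 days, but the SAP text supplied specifies a between-arm test only of contraceptive use at 30 days

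*Protocol*

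**What the plan says.** Protocol 2.0 gives the purpose of the limited-efficacy comparison: "we compare two arms (MLI vs. eSOC) to determine size of effect rates on contraception initiation". Hypothesis 1.2 in the same section reads "Adolescents in the MLI arm will have greater contraception initiation rates relative to the eSOC arm at 30 days after the index ED visit". Protocol 4.0 lists initiation as a secondary endpoint and, under Hypothesis 1.2, treats it as a dated event: "We will determine referral completion and date for contraception initiation (Time 0) via participant contact and review of study/medical records at thirty days". Initiation is not the only efficacy quantity named. The limited-efficacy row of Table 1 also asks for continuation and referral completion, and the note to Table 1 repeats all three.

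The SAP describes "Fisher exact tests to compare arms on the percent of participants using contraception at 30 days", by intention to treat. Its missing-data rule is also framed as use: "Dropouts during the index visit were treated as having no subsequent contraceptive use". The only other between-arm comparison it specifies is of change scores such as attitudes. Initiation and referral completion do not appear in the SAP text supplied. Part of the SAP file was not available to this review, so the point applies to the supplied text only.

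Two design features bear on this. Protocol 11.0 excludes "Females who are currently using hormonal contraception or the copper intrauterine device". Protocol 6.0 lets MLI participants receive a method in the ED ("one injection, three-month supply of pill/patch/ring, or subdermal implant"), while for eSOC it says "Subjects in this group will not begin contraception in the Emergency Department or given a prescription"; Protocol 1.0 confines eSOC access to the referral.

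**The concern.** Having started a method by day 30 is an event. Using a method at day 30 is a status. They differ for anyone who starts and then stops within the month, and that loss need not be equal between arms. An MLI participant who starts in the ED has up to 30 days in which to stop; an eSOC participant who starts at a later clinic visit has fewer. The difference in use is then the difference in initiation net of early stopping, which is not the effect size Protocol 2.0 set out to obtain.

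There is a second, smaller gap. Neither document ties the outcome to a list of methods. The exclusion covers hormonal methods and the copper IUD but not condoms, so a participant who used condoms at entry could count as using contraception at day 30 without having initiated anything.

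At stake is the effect estimate that would be carried into planning a later trial. The feasibility endpoint does not depend on it.

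**Working it through.** **Text comparison**

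| Item | Protocol | SAP text supplied |
|---|---|---|
| Outcome | Initiation (2.0, 4.0) | Use |
| Type | Dated event, Time 0 | Status |
| Timing | Determined at 30 days | At 30 days |
| Referral completion | Named (4.0, Table 1) | No between-arm analysis |
| Method list for the outcome | None | None |

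**How close the two measures are.** For the excluded methods, nobody is a user at entry. Use at day 30 therefore implies initiation, but initiation does not imply use at day 30. Write p for the initiation rate and d for the share of starters who have stopped by day 30, with subscripts M (MLI) and E (eSOC):

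use difference = p_M(1 − d_M) − p_E(1 − d_E) = (p_M − p_E) − (p_M·d_M − p_E·d_E).

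If MLI has the higher initiation rate, the use difference is the smaller one unless d_E/d_M exceeds p_M/p_E.

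**Inputs.** The documents give no assumed rates, alpha, power or effect size behind the 98 adolescents, so there is no planned figure to reproduce. Everything below is illustration:
- p_E = 22%, borrowed from the referral completion that Protocol 3.0 reports for an earlier open trial; it is not an initiation rate.
- p_M = 50%, assumed, with 40% and 60% as a range.
- d assumed from 0% to 30%.
- 49 per arm, from 98 randomised 1:1.

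The n per arm for a later trial uses the pooled two-proportion formula, without continuity correction, at 80% power and an assumed two-sided 5% level:

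n = [1.96·√(2p̄(1−p̄)) + 0.84·√(p₁(1−p₁)+p₂(1−p₂))]² / (p₁−p₂)².

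| Stopped by day 30 (MLI / eSOC) | Use, MLI vs eSOC | Difference | n per arm |
|---|---|---|---|
| 0% / 0% | 50.0% vs 22.0% | 28.0 points | 45 |
| 5% / 5% | 47.5% vs 20.9% | 26.6 | 49 |
| 10% / 10% | 45.0% vs 19.8% | 25.2 | 53 |
| 20% / 20% | 40.0% vs 17.6% | 22.4 | 63 |
| 30% / 30% | 35.0% vs 15.4% | 19.6 | 76 |
| 5% / 2% | 47.5% vs 21.6% | 25.9 | 52 |
| 20% / 10% | 40.0% vs 19.8% | 20.2 | 80 |

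At these rates p_M/p_E = 50/22 = 2.3, so eSOC stopping would have to exceed 2.3 times MLI stopping before the use difference became the larger one.

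Varying p_M, with 20% stopping in both arms:
- p_M = 40%: the difference goes from 18.0 to 14.4 points (103 to 140 per arm).
- p_M = 60%: it goes from 38.0 to 30.4 points (26 to 37 per arm).

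**Against sampling error.** With 25/49 versus 11/49 initiating, the difference is 28.6 points, Newcombe 95% CI 9.5 to 45.0. The largest shift in the table is 28.0 − 19.6 = 8.4 points, well inside that interval. The reported P value can still move: 25/49 versus 11/49 gives Fisher P = 0.006, and if 5 MLI and 1 eSOC starters have stopped, 20/49 versus 10/49 gives P = 0.048.

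**Condoms.** If the same share c of non-initiators in each arm counts as using, each rate becomes p + c(1 − p), and the difference is multiplied by (1 − c). This also shrinks it. The documents give no value for c.

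**The case against.** The best defence is that the SAP has simply made the outcome operational. A rate of initiation at 30 days can be read as status at 30 days, and the exclusion of current users makes the two nearly the same. Continuation is itself named in Table 1, so use at day 30 is not foreign to the Protocol. The injection, the implant and a three-month supply in hand all leave limited room for early stopping. Early stopping would usually understate the MLI effect, so the choice does not flatter the intervention.

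Most of this stands. The measure is a close proxy, and the gap may be trivial. What does not stand is the claim that the two are one outcome: Protocol 4.0 asks for an initiation date, Table 1 names initiation and continuation as distinct quantities, and the supplied SAP text neither equates use with initiation nor gives a reason for the change.

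A reader might infer more: that initiation has been dropped and will go unreported, or that the outcome was switched to favour MLI. The documents do not support either. The note to Table 1 still lists initiation, continuation and referral-completion rates among the planned assessments, and nothing in the SAP withdraws them. The likely direction of the shift is against MLI.

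**Conclusion.** The point holds as a discrepancy in outcome definition. The Protocol sets initiation, determined at 30 days, as an outcome of the between-arm efficacy comparison; the SAP text supplied specifies a test of use at 30 days and no between-arm analysis of initiation or of referral completion.

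Its size is unknown. In the illustration it runs from about 1 point (5% stopping in both arms) to about 8 points (30% in both arms, or 20% in MLI and 10% in eSOC). For a later trial that is 49 to 80 per arm instead of 45. These figures rest on assumed initiation and stopping rates, and on a referral-completion rate standing in for eSOC initiation. The expectation that loss is greater in MLI rests on the earlier possible start in that arm, not on data.

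Within this trial the shift lies inside sampling error. The outcome is secondary, and the feasibility conclusion does not change. It would be wrong to infer that the efficacy comparison is invalid, because use at day 30 remains informative. Severity is minor to should-fix.

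**What to change.** Add to the SAP a Fisher exact test and effect size for initiation of a qualifying method by day 30, among all randomised participants, with participant contact and record review applied in the same way in both arms. Restate the index-visit dropout rule for that outcome. Keep use of the same methods at day 30 beside it, on the same denominator.

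Give one list of qualifying methods for both measures. Say how condoms, emergency contraception, non-hormonal gel and IUDs are classed for the outcome, count only methods not in use at baseline, and report condom use separately. State also how referral completion will be compared between arms.

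The SAP is written in the past tense, so label the initiation analysis as specified in the Protocol but added to the SAP. If the move to use was deliberate, disclose it as a deviation with the reason, leave Hypothesis 1.2 as written, and still report initiation counts by arm.

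The cost is a few sentences, an extra row for initiation in the efficacy table, and two 30-day rates to explain. Protocol 4.0 already plans to obtain the initiation date. The survey forms are not in the documents, so it should be checked that they capture both start date and current method.

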3.0 Background

Unintended adolescent pregnancy is a major public health problem linked to pregnancy-induced hypertension, low birthweight, and prematurity.¹⁻² In addition, adolescent pregnancies cost an estimated \$9.4 billion annually.³⁻⁴ Though declining, U.S. rates remain among the highest in the developed world.⁵⁻⁷ Highly effective methods exist, but adolescents face unique, multi-level barriers to contraceptive access and use.³⁻⁴ Thus, the vast majority of pregnancies are due to contraceptive non-use or incorrect use.⁵ Many, especially minority and uninsured youth, do not attend health maintenance visits;⁶ among those who do, 36 seconds is spent discussing sexuality and contraceptive use is not routinely assessed.⁶ Multi-level interventions to increase access to contraceptive counseling and all contraceptive types are desperately needed.⁷

As adolescent access to affordable, confidential contraceptive care has worsened in recent years, one approach to increase access is to utilize non-traditional settings, such as Emergency Departments (EDs).⁷ The Society for Academic Medicine recognizes the ED as an “effective site for preventive care,” evidenced by organizational conferences, consensus statements, and specialized training opportunities to reduce disparities stemming from social determinants of health.⁸⁻¹¹ Adolescents make 19 million ED visits annually, commonly for non-urgent or reproductive complaints; for many, this may be their only contact with a provider.¹²⁻¹⁴ Adolescents in the ED frequently report unprotected intercourse.^{25,40} The pregnancy risk index (PRI), an estimate of pregnancy risk in the subsequent 12 months, for adolescent females in two EDs was more than three times greater than the national average.¹⁵⁻¹⁶ Lacking a primary provider was associated with higher PRI scores. While the need for reproductive care is evident,^{17,18} the majority of ED-based studies have focused on screening for sexually transmitted infections (STIs) including HIV¹⁹⁻²⁰ and a few, primarily single-site studies have reported on acceptability of hypothetical reproductive care.^{21,22-26} Among the few addressing pregnancy prevention, most focused on emergency contraception or increasing clinic referral, with mixed results.^{27,28-31} A small open trial provided counseling and clinic referral for those wanting to initiate contraception. Only 22% completed the referral and one was found to be pregnant at her first clinic visit.³² Lack of transportation was the most common reason for not completing referral. Because interventions to address multi-level barriers and

SHORT TITLE: Reducing Pregnancy in the ED

increase contraception access are sorely needed, we aim to evaluate the feasibility of a novel ED-based intervention, utilizing a mixed methods approach.

Scientific Premise: Many adolescents in the ED are at high-risk of pregnancy yet accepting of reproductive intervention; however, no work describes best practices for ED-based contraceptive provision. Thus, we propose a randomized trial to evaluate MLI, which includes ED-based contraceptive initiation (i.e., oral pill, transdermal patch, vaginal ring, injection, or subdermal implant) vs. eSOC, for adolescents in two EDs utilizing medical providers in a collaborative care model. Thus, we use a rigorous framework from Bowen et al. to evaluate feasibility constructs (see Table 1 for construct definitions) among adolescents and organizational personnel (i.e., medical providers, adolescent medicine specialists, ED nursing and administrative leaders) in two unique EDs.³³

